#### 6. STUDY ENDPOINTS

#### 6.1 PRIMARY ENDPOINTS

#### **6.1.1 Primary Safety/ Tolerability Endpoints:**

- Safety/Tolerability will be assessed by the non-inferiority of incidence of serious adverse events (SAEs), unanticipated SAES (USAEs), device-related SAEs (DSAEs) and Unanticipated Device Related SAEs (UDAEs) that are associated with the TENS therapy throughout the therapy/treatment period versus historical control.
- Safety variables will be tabulated and presented for all subjects including enrolled, but discontinued, subjects. Number of subjects undergoing TENS and any reasons for discontinuation of study treatment will be tabulated.

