## Study Endpoints

#### Primary Safety/Tolerability Endpoint:

Safety/Tolerability will be assessed by the non-inferiority of incidence of serious adverse events (SAEs), unanticipated SAEs(USAEs), device-related SAEs (DSAEs) and Unanticipated Device Related SAEs (UDAEs) that are associated with the TENS therapy throughout the stimulation and the follow-up period versus historical control (compared with other TENS systems).

Safety variables will be tabulated and presented for all subjects including enrolled, but discontinued, subjects. Number of subjects undergoing active stimulation and any reasons for discontinuation of study treatment will be tabulated.

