#### Risk/Benefit Analysis

If shown to be safe and effective, the therapy could eventually provide overweight/ moderately obese subjects a low risk option for weight control beyond diet and lifestyle modification alone.

The potential adverse events and adverse device effects and risks associated with this study and the use of the patch System are identical to those normally associated with standard TENS system used for pain control and similar indications.

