#### 8.1.1 Safety/Tolerability

The primary safety endpoint is defined as the proportion of subjects free of TENS - related serious adverse events and/or adverse device effects through the therapy phase (safety success rate). The AE and/or ADE rates will be summarized utilizing descriptive statistics and compared utilizing parametric and non-parametric methods as deemed appropriate. The null and alternative hypotheses are:

```
H_0: π_T ≤ π_C
H_1: π_T > π_{C}
```

Where  $\pi_T$  and  $\pi_C$  are the probabilities of adverse events and/or adverse device effects in treatment versus historical control respectively.

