#### 10.1.2 Risks associated with appetite loss

While appetite loss is beneficial to weight loss, severe appetite suppression may place the subject at risk for hypoglycemia and dehydration which may entail risks to alertness and other conditions. Prolonged appetite suppression can cause alterations in mood and mental acuity and impact activities of daily living (ADL).

Adverse Events: The adverse events listed below are anticipated to occur at low frequency, and the subject needs to be aware that they may occur.

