#### 10.2 MINIMIZATION OF RISKS

Although all of the risks associated with the application and use of the TENS System and their respective frequencies may not be fully known at this time, the preceding risks have been identified through an extensive literature search and represent the most up to date understanding of risks associated with such a study and have been subjected to verification and validation testing to ensure that risks have been mitigated to the extent possible. All efforts will be made throughout the course of the trial to minimize these risks by:

- 1. Selecting an Investigator who is experienced and skilled in weight loss and TENS use:
- 2. Using clearly defined Inclusion/Exclusion criteria to ensure that only appropriate subjects are enrolled;
- 3. Ensuring that the treatment and follow-up procedures are consistent with current medical practices. Each subject will receive more extensive clinical follow-up than would typically be the case for standard care. These additional clinical follow-ups should increase the likelihood of early detection of any adverse events:
- 4. Utilizing a TENS designed so that it can be easily be applied and removed if necessary.

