#### 11.2 UNANTICIPATED ADVERSE DEVICE EFFECTS

An unanticipated adverse device effect is defined as any adverse effect on health or safety or any life-threatening problem or death caused by, or associated with, a device, if that effect, problem, or death was not previously identified in the Protocol or Supplementary Protocol.

The Investigator must also report the unanticipated adverse device effect to the Institutional Review Board (IRB) within their pre-specified timeline.

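### The primary safety non-inferiority comparison includes two unanticipated event classes whose rate depends on this protocol's own risk list, and section 8.1.1 defines the endpoint without them

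*Combined protocol and SAP*

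**What the plan says.** The Protocol Summary (Primary Safety/Tolerability Endpoint) and section 6.1.1 use non-inferiority of event incidence as the primary safety criterion. Four classes are named: SAEs, and then "unanticipated SAES (USAEs), device-related SAEs (DSAEs) and Unanticipated Device Related SAEs (UDAEs) that are associated with the TENS therapy throughout the therapy/treatment period versus historical" data. The Summary identifies the comparator: "versus historical control (compared with other TENS systems").

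The term unanticipated is defined once, in section 11.2, and only for an adverse device effect. An effect qualifies "if that effect, problem, or death was not previously identified in the Protocol or Supplementary Protocol". The class abbreviated USAE, which need not be device-related, has no definition. UDAE has none under that name.

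The events this Protocol identifies are listed under section 10.1.2, introduced by "The adverse events listed below are anticipated to occur at low frequency". The list is grouped by source: TENS, appetite loss, anti-nausea medication and moisturizing lotion. Section 10.2 says "the preceding risks have been identified through an extensive literature search". The Risk/Benefit Analysis in the Summary says the risks "are identical to those normally associated with standard TENS system used for pain control and similar indications".

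Section 8.1.1 defines the primary safety endpoint differently, as "the proportion of subjects free of TENS - related serious adverse events and/or adverse device effects through the therapy phase (safety success rate"). It has no unanticipated class. No historical source, rate or non-inferiority margin is given for any class.

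**The concern.** Whether an event is unanticipated is not a property of the harm. It is a relation between the event and a document. Here the document is this Protocol; in a historical TENS study it would be that study's own protocol or labelling. Two unanticipated rates based on different lists do not measure the same thing, so a difference between them need not be a difference in safety.

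For two of the four named classes the result would therefore depend partly on how the risk list was written. A longer list gives fewer unanticipated events in the treatment arm for the same harm. Supplying a historical rate and a margin would make the test computable but would not remove this dependence.

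The conflict with section 8.1.1 adds to the difficulty. A reader cannot tell whether the unanticipated classes are formally tested, and the choice could end up being made after the safety data are known.

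**Working it through.** The plan states no safety sample size, power, margin, alpha or historical rate, so there is no safety figure to reproduce. The check has three steps.

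**1. Is the classification shared by both sides of the comparison?**

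| Item | This trial | Other TENS systems |
|---|---|---|
| Reference for unanticipated device effects | This Protocol or its supplement (11.2) | Not stated; a published rate would use its own list |
| Reference for USAE | None given | Not stated |
| Sources on the risk list | TENS, appetite loss, anti-nausea medication, lotion (10.1.2) | Not stated; general TENS use need not share the last three |
| Event-level data for re-coding | Collected in the trial | No source named |

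The statement that risks are identical to standard TENS concerns which harms occur. It does not show that past events were classified against this list. Re-coding historical events against the list would put both sides on one definition, but it needs event-level records. Because the list came from a literature search, the re-coded rate would probably be low, though not necessarily zero.

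**2. What can the trial say about these classes?**

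Inputs: 75 treated (section 8.2), or 150 treated if the trial expands to the 300 in the Protocol Summary with equal arms. With 0 events the exact (Clopper-Pearson) two-sided 95% upper limit is 1 − 0.025^(1/n).

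- n = 75: 1 − 0.025^(1/75) = 4.80%
- n = 150: 1 − 0.025^(1/150) = 2.43%

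With 1 event the exact limits are 7.21% and 3.66%. These bounds need no historical rate.

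**3. How far could the list alone move a result?**

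This is an illustration only, because the documents give neither a margin nor a rate. Assume 75 treated, a fixed historical rate between 0 and 2%, an absolute margin of 5 points, and a pass when the upper limit is below rate plus margin. The threshold then lies between 5% and 7%.

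- One unlisted event: 1/75 = 1.33%, upper limit 7.21%. This fails across the range.
- The same event with its term on the list: 0/75, upper limit 4.80%. This passes across the range.

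The harm is the same in both cases. The switch depends on the assumed margin. A 2-point margin is not met even with 0 events anywhere in this range, because its threshold is at most 4%. A 10-point margin tolerates 2 events at a historical rate of 0 (limit 9.30%), so one re-labelled event would matter only near that boundary.

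**The case against.** The strongest reply is that section 8.1.1 is the statistical section, that it names a single composite with no unanticipated class, and that the unanticipated classes may therefore never be tested. That is a fair reading, but the Summary and 6.1.1 say otherwise in the endpoint definition itself. The reply makes the conflict part of the point; it does not remove it.

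A reader might go further than the documents allow in several ways.

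- **The historical rate is zero by construction, or no such rate exists.** Not supported. Section 10.2 itself concedes that the risks and their frequencies may not be fully known, and many listed TENS and appetite items are mild symptoms. A historical device-related SAE outside the list would count as unanticipated. The historical source is unnamed, so nobody can say what it contains.
- **The claim cannot be decided, or no ratio margin could be met.** Not supported. Even against a rate of zero an absolute margin can be tested, as step 3 shows, and the documents propose no ratio margin.
- **The chance of seeing at least one unlisted event is the chance of failing.** It is not. Non-inferiority depends on the upper limit against rate plus margin, not on exceeding the comparator's observed rate.
- **SAE and device-related SAE are one class.** The words restricting events to those associated with TENS may apply to all four classes or only to the last. The sentence is ambiguous, and the sponsor should say which is meant.

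It also stands that for USAE the fault is first a missing definition, since section 11.2 covers device effects only. The absence of a historical rate and margin affects all the classes and is not specific to these two.

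**Conclusion.** The point holds in a limited form. Two of the four classes in the primary safety comparison are list-dependent or undefined, so a comparison with other TENS systems on those classes would partly reflect the completeness of the risk list. A rate and a margin alone would not cure that. The Summary and 6.1.1 also disagree with 8.1.1 on what is tested.

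The conclusion rests on the text of 11.2 and on the absence of a named event-level historical source. If such a source exists and is re-coded against this list, the comparison becomes possible, but it still moves with the list. For scale, 0 events bounds either class at 4.8% with 75 treated, or 2.4% with 150. The size of any effect on the primary safety conclusion cannot be given without a rate and margin.

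**What to change.** - In the Protocol Summary and section 6.1.1, remove USAE and UDAE from the historical non-inferiority comparison. Align the tested endpoint with the class in 8.1.1, keeping the adverse device effects named there. Narrowing it to serious events would drop part of the endpoint.
- Define USAE, and tie UDAE to the definition in 11.2. Report both as counts and proportions of treated subjects, with exact 95% confidence intervals and individual narratives. Leave safety reporting unchanged.

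The cost is wording only, with no new data, visits or subjects. The small downside is that unanticipated events are described and not tested. This change does not supply the historical source, rate or margin for the remaining comparison; those still have to be stated separately.

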#### 6.1.2 Primary Effectiveness Endpoint:

The primary effectiveness endpoint is the percent reduction in total body weight loss (%TBWL), measured as End Weight – Initial Weight divided by Initial Weight, multiplied by 100, at the end of Therapy period compared to Baseline between Treatment and Control.

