#### Primary Effectiveness Endpoint:

The primary efficacy endpoint is the percent reduction in total body weight loss (%TBWL), measured as End Weight – Initial Weight divided by Initial Weight, multiplied by 100, at the end of Therapy period compared to Baseline between Treatment and Control.

Secondary Effectiveness Endpoints:

Number of subjects reporting >5% total body weight loss at the end of Therapy compared to Baseline between Treatment and Control

Percent change in appetite scores at the end of Therapy period compared to Baseline between Treatment and Control.

Blood pressure, blood lipids, CMP (Reduction in ALT) and HbA1c at the end of Therapy compared to Baseline between Treatment and Control groups.

% changes in BMI at the end of Therapy compared to Baseline between Treatment and Control groups

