#### 6.1.3 Secondary Effectiveness Endpoints:

- Number of subjects reporting >5% total body weight loss at the end of Therapy as compared to Baseline between Treatment and Control
- Percent change in appetite scores at the end of Therapy Period compared to Baseline between Treatment and Control.
- Blood pressure, blood lipids, ALT and HbA1c at the end of Therapy Period as compared to Baseline between Treatment and Control groups.
- % changes in BMI at the end of Therapy Period compared to Baseline between Treatment and Control groups

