#### 8.1.3 Weight Loss

The null and alternative hypotheses are:

$$H_0$$
:  $π_T ≤ π_C$ 
 $H_1$ :  $π_T > π_C$ 

Where  $\pi_T$  and  $\pi_C$  are the probabilities of weight loss (% TBWL, %EBWL) in treatment versus control respectively. Estimates of the proportion of weight loss in pounds, % total body weight loss (%TBWL) Excess Body Weight Loss (%EBWL) or BMI will be compared with a tested Fishers Exact Test. Estimates and 95% confidence intervals will also be computed for the difference in rate of weight loss between varying stimulation levels.

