#### 8.2 JUSTIFICATION OF SAMPLE SIZE

The calculated sample size for the study is based on conservative imputation of results from other studies on weight loss including the use of TENS for weight loss. The degree of coaching/dietary support throughout the present study is moderate intensity lifestyle/weight coaching. The sample size modeling assumes an average of 3.5% TBWL in Control subjects using diet and exercise alone. The estimated weight loss in the Treatment subjects is modeled from preliminary data on T6/T7 dermatomal TENS when used for weight loss: 7.5% TBWL. The variance of the responses in the study (i.e. Standard Deviation) was modeled at + 5% TBWL. This value was taken from previous dermatomal TENS weight loss study results. The model assumes a 30% drop out rate across groups and an 80% powered endpoint using an adaptive p spending model wherein interim posterior probability assessments are allowed after enrolling proscribe cohorts of not less than 25 subjects per group for not less than 7 weeks of stimulation. The alpha penalty will be minimized per interim by assessing the relationship between stimulation (i.e. dose) and weight loss using Normalized Linear Dynamic Modeling (NLDM) to determine overall sample size projected (i.e. futility) rather than assessing the primary endpoint hypothesis per se. Monotonicity will not be assumed in this analysis. This modeling provides an estimate of 75 subjects per group, for a total study size of 150 subjects. However, the protocol allows for enrollment of additional subjects should the interim model project under powering of the primary endpoint.

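### The primary endpoint formula gives weight loss a negative sign, contradicting its own label, the planning values and the >5% loss threshold

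*Combined protocol and SAP*

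**What the plan says.** The Protocol Summary (Primary Effectiveness Endpoint) and Section 6.1.2 carry the same definition. The label is "the percent reduction in total body weight loss (%TBWL"), and the formula is "measured as End Weight – Initial Weight divided by Initial Weight, multiplied by 100". This is the only definition of %TBWL in the documents.

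Four other places use the same quantity or a related one:

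- Section 8.2 writes it as a positive number: "The sample size modeling assumes an average of 3.5% TBWL in Control subjects", with 7.5% in Treatment and a standard deviation of 5%.
- Section 6.1.3 and the Protocol Summary count responders as "Number of subjects reporting >5% total body weight loss at the end of Therapy".
- Section 8.1.3 states the alternative as π_T > π_C, where these "are the probabilities of weight loss (% TBWL, %EBWL) in treatment versus control respectively". The estimates "will be compared with a tested Fishers Exact Test".
- Section 8 provides two-sided 95% confidence intervals for differences in means, and posterior probability assessments of efficacy within and between cohorts.

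The Visit Schedule and Appendix 6 record weight at both Visit 0 (screening/baseline) and Visit 1 (enrollment/randomization). Neither definition says which of the two is the initial weight.

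**The concern.** The formula and its label disagree within one sentence. A reduction or a loss is positive when weight falls; end minus initial is negative. The label is itself garbled, since a reduction in a loss would mean less weight lost. The formula also has no parentheses: by strict operator order it reads End - (Initial / Initial) x 100 = End - 100, which is not a percent change at all.

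An analyst has to choose between the formula and its label for the primary endpoint of a study that the Protocol Summary describes as pivotal. The choice matters wherever direction enters the analysis:

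- a one-directional comparison of arms;
- an interim posterior probability that one arm exceeds the other (the exact posterior quantity is not specified);
- the correlation of stimulation parameters with endpoint values (Section 8), which changes sign;
- any cut-off on %TBWL, including one used for the imputation as success or failure in Section 8.3, where neither term is defined.

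**Working it through.** **Inputs.** Section 8.2: control mean 3.5, treatment mean 7.5, SD 5, 75 per group, 30% dropout, 80% power. Section 6.1.2: the formula. No test alpha is stated, so 0.05 two-sided is assumed from the 95% intervals in Section 8. The responder shares below also assume normally distributed %TBWL.

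**Sample size and sign.** For two means, n per arm = 2 x (1.96 + 0.842)² x SD² / δ² = 2 x 7.85 x 25 / 16 = 24.5, so 25, and 25 / 0.7 = 35.7, so 36 after dropout. This does not reproduce 75 per group. The adaptive model behind 75 is not specified, and that is a separate matter. For the sign, what counts is that δ enters squared: +4 and -4 give the same n.

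**Planning values in the two forms.**

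| | Treatment | Control | Difference |
|---|---|---|---|
| Section 8.2 | +7.5 | +3.5 | +4.0 |
| Section 6.1.2 formula, with parentheses supplied | -7.5 | -3.5 | -4.0 |

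**Two-sided interval (Section 8).** With 75 per arm, SE = 5 x √(2/75) = 0.816. The expected interval for the signed difference is -4.0 ± 1.96 x 0.816, or -5.6 to -2.4. It excludes zero, and a reader who knows the sign will interpret it correctly.

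**Hypothesis and responder rule read in words.** Here the quantity is an amount of loss, whatever the sign of the formula.

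- Share losing more than 5%: Treatment 1 - Φ((5 - 7.5)/5) = 69.1%; Control 1 - Φ((5 - 3.5)/5) = 38.2%. Two-sided Fisher power is 96.6% at 75 per arm and 87.6% at 52 per arm (75 x 0.7 = 52.5).
- Share losing any weight: Φ(7.5/5) = 93.3% versus Φ(3.5/5) = 75.8%. Two-sided Fisher power is 81.6% at 75 per arm.

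Both comparisons favour Treatment, as intended.

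**Signed variable used mechanically.** These results are conditional on an analyst taking the defined variable into a directional rule.

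- Treatment greater than control on means: z = -4.0 / 0.816 = -4.90 at 75 per arm. At 52 per arm, SE = 5 x √(2/52) = 0.981 and z = -4.08. A device that works as planned points the wrong way.
- Values above +5 counted as responders: 1 - Φ((5 + 7.5)/5) = 0.6% versus 1 - Φ((5 + 3.5)/5) = 4.5%. These subjects are weight gainers.

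**The case against.** The strongest reply is that nothing the plan specifies in words goes wrong. Section 8.1.3 puts its hypothesis on probabilities of weight loss and names Fisher's exact test; a probability of losing weight is higher when the device works, whatever the sign of a formula elsewhere. The responder rule says loss in words and does not cite the formula. For means, Section 8 gives two-sided intervals. The label, the positive planning values and the whole purpose of the trial leave no doubt that more loss is better, and any reader already has to supply the missing parentheses.

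This stands as far as it goes. A reader might infer from the formula and the direction of H1 that a working device fails the test as written. The documents do not support that. No section specifies a directional test on the mean of the signed variable, so z = -4.90 belongs to a comparison that the plan does not contain. The >5% rule is also a secondary endpoint, so it cannot make the primary test fail.

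What the reply does not remove is the contradiction itself. The reading in words works only by setting aside the sole definition of %TBWL, and Section 8.1.3 names that same variable in its hypothesis. The planned posterior probabilities are not specified closely enough to rule out a directional statement on the signed value.

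**Conclusion.** The concern holds as a sign error in the definition of the primary endpoint, present in both the Protocol Summary and Section 6.1.2. At the planning values it turns +7.5 and +3.5 into -7.5 and -3.5. The required sample size is unaffected, as are the hypothesis and responder rule when read in words. A reversed conclusion would need the signed variable to be carried into a directional comparison, a directional posterior probability or a cut-off at 5. The documents prescribe none of these on the signed value, but they do not exclude them. The responder shares rest on normality and on the means and SD in Section 8.2; the sign conflict rests on no assumption.

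Section 8.1.3 also shows a related mismatch that should be settled in the same edit: the endpoint is continuous and planned on means and an SD, while its hypothesis and test are for proportions with no stated cut-off.

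**What to change.** 1. In the Protocol Summary and Section 6.1.2, define %TBWL = 100 x (Initial Weight - End Weight) / Initial Weight, with parentheses, and call it percent total body weight loss, without the words about a reduction in loss.
2. In Section 8.1.3, state the primary alternative as mean %TBWL greater in Treatment than in Control, so that it matches the endpoint and the basis of Section 8.2, and name a comparison of means for it. Fisher's exact test can then serve the responder endpoint.
3. In Section 6.1.3 and the Protocol Summary, define a responder as %TBWL > 5 on the same variable.
4. State which pre-treatment weight, Visit 0 or Visit 1, is the initial weight. The documents label Visit 0 as screening/baseline and also weigh subjects at Visit 1, so either choice is open but must be fixed in advance.

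The cost is wording only. Items 1, 3 and 4 are clarifications; item 2 changes the stated primary hypothesis and test and should be made before any interim look at outcome data. No new data are needed, and the sign correction does not change the required sample size.
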